After appropriate patient consent and preparation, we will randomize the order in which the patient will receive the Standard of Care PET/CT and the Low Dose PET/CT (i.e. Standard of Care PET/CT on day 1 and Low Dose PET/CT on day 2, or vice versa). If the patient has requested to opt out of the additional whole-body sweep, the patient will be imaged at both examination days at 75 min +/- 10 min post injection. Otherwise, the patient imaging will start with the voluntary whole-body sweep at 60 min +/- 10 min, followed by the standard of care whole-body sweep at 75 min +/- 10 min.

It is well established that the image quality in patients that are classified by the WHO Body Mass Index (BMI) criteria as \Rightarrow obese (BMI \Rightarrow 30) is reduced and that longer bed volume acquisition times improves image quality [JNM Tech 2014 Sanchez-Jurado]. We will therefore increase the otherwise constant acquisition time per bed volume from 90 s to 120 s in those patients for both dose levels.

Using segmented reconstruction, we will be able to down sample the acquisition to be simulated as a 90 s acquisition for overall consistency.

As we are using four different current technology PET/CT systems, we will perform 4 sub-studies that are otherwise fully equivalent.

Sub-Study A: 481 MBq (13 mCi) ¹⁸F-FDG vs. 185 MBq (5 mCi) using Gemini Astonish PET/CT

Sub-Study B: 481 MBq (13 mCi) ¹⁸F-FDG vs. 185 MBq (5 mCi) using Biograph mCT **Sub-Study C:** 481 MBq (13 mCi) ¹⁸F-FDG vs. 185 MBq (5 mCi) using Discovery PET/CT

Sub-Study D: 481 MBq (13 mCi) ¹⁸F-FDG vs. 185 MBq (5 mCi) using Vereos 128 digital PET/CT

We are furthermore planning two additional sub-studies.

Current simulations indicate that we should be able to further reduce the FDG imaging pharmaceutical dose to an even lower level. We will determine that comparison level after completing of Sub-Study D. At this time we would assume that the clinical SOC dose would have been already reduced to 240.5 MBq (6.5 mCi), and we would then compare it to 92.5 MBq (2.5 mCi).

Sub-Study E: 241 MBq (6.5 mCi) ¹⁸F-FDG vs. 93 MBq (2.5 mCi) using Vereos 128 digital PET/CT

We plan for the possibility that one of the three-Sub-Studies (A-B) would not demonstrate equivalency, and we would then perform a modified protocol in which the SOC dosing is compared to a lower and higher dose than originally tested.

Sub-Study F: 481 MBq (13 mCi) ¹⁸F-FDG vs. tbd MBq using the system that did not show equivalency in Sub-Study A-C

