Figure 1 charts the study protocol and randomization.

[figure not shown]

Figure 1: Flowchart of the protocol. After consent, the subject is randomized to the order of low and standard of care dose PET/CT. If the patient opts out of the second whole-body sweep, both exams will be performed at 75 min +/- 10 min p.i., otherwise the 1st sweep will be performed at 60 min +/- 10 min, followed by the 2nd at 75 min +/- 10 min.

Sample Size Considerations

The project statistician has calculated a required sample size of 33 evaluable subjects per imaging modality if we assess tracer uptake (FDG) using both a quantitative (SUVmax) and a visual quality assessment. Based on the literature and our preliminary work, we assume that the coefficient of variation (COV) is 12% and the equivalence limit is 10%. With a total sample size of 33 patients we will achieve 80% power in an equivalence test of means using two one-sided tests (TOST) on data from a two-period cross-over design, using an alpha level of 0.025 (0.05/2) after Bonferroni adjustment each system, respectively. We assume a drop-out rate of 10% (4 subjects) which leads to our target population of 37 enrolled subjects per unique sub-study.

Four imaging systems will be utilized in this study:

- Gemini TOF Astonish system from Philips Healthcare Cleveland
- Biograph mCT from Siemens Knoxville
- Discovery PET/CT from General Electric, Milwaukee
- Vereos 128 PET/CT from Philips Healthcare Cleveland (this is the first commercial digital PET detector system)

The subjects imaged at each of the four PET/CT systems will treated as its own sub-study. Each sub-study will follow the same imaging protocol.

We will evaluate four different state of the art PET/CT system in the above defined six sub-studies which then leads to the overall study population estimate of 204 subjects.

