- Patients unable to lie flat on the scanner for extended periods of time.

Measurement / Instrumentation

Our assessment approaches will be guided by recent community efforts established via the QIBA (RSNA) effort, PET recommendations (SNM), the QIN (NCI) and IROC (NCTN).

In this study, we will not evaluate the impact of the CT-based attenuation scan, as in recent years extensive efforts in CT dose reduction have also translated to substantially lower CT doses for attenuation scans, unless diagnostic read quality is needed to simultaneously replace an additional diagnostic CT scan. We will perform all CT-based attenuation scans at the lowest dose we established for our standard of care PET/CT protocol for each specific PET/CT system.

We currently have four different state of the art PET/CT systems within the OSU Wexner Medical Center. We therefore plan to perform this trial in four separate sub-studies, each being independent for each device, with everything else being standardized. With this unique ability to evaluate the dose and timing impact and to prove equivalency using four distinct platforms in parallel, we will achieve the most meaningful outcome and impact. This will allow us to achieve the desired changes of reducing radiation dose and enabling more flexibility in the imaging time post injection.

The imaging data will be assessed in a fully blinded fashion. Our primary endpoint will be the statistical confirmation that the SUV max measured in the regions of interest (ROI) in the target region will reveal a variation of less than 10%. The project statistician has calculated a required sample size of 37 evaluable subjects per sub-study (See section Statistical Considerations). We will treat each of the four PET/CT system as its own sub-study; however, we will perform each of the first four sub-studies identically other than the manufacturer system-induced differences.

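### The stated total of 204 subjects does not follow from 37 enrolled per sub-study: six sub-studies need 222, and five (without contingent Sub-Study F) need 185

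*Protocol*

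**What the plan says.** All references are to section IV (Procedures) of the protocol.

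- **Sample Size Considerations** gives a "required sample size of 33 evaluable subjects per imaging modality". It adds a 10% drop-out allowance of 4 subjects, which "leads to our target population of 37 enrolled subjects per unique sub-study". The same section closes by saying that the four systems are studied "in the above defined six sub-studies which then leads to the overall study population estimate of 204 subjects".
- **Research Design** defines the six. Sub-Studies A to D cover one scanner each, E is an additional dose comparison on the Vereos system, and F is conditional: "We plan for the possibility that one of the three-Sub-Studies (A-B) would not demonstrate equivalency". In that event F would follow a modified protocol in which the "SOC dosing is compared to a lower and higher dose than originally tested".
- **Measurement / Instrumentation** restates the per-sub-study number differently, as a "required sample size of 37 evaluable subjects per sub-study".

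The protocol gives no smaller number for E or F and describes no sharing of subjects between sub-studies.

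**The concern.** The text presents 204 as the result of applying the per-sub-study number to six sub-studies, but the multiplication gives 222. Because F is conditional, one might suppose that 204 leaves it out, but five sub-studies need 185. The total is therefore too low for one case and too high for the other.

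Power is planned separately for each system, so spare subjects in one sub-study cannot make up a shortfall in another. If 204 acts as the enrolment limit and all six sub-studies run, at least one of them is expected to fall below 33 evaluable subjects. Sub-Study F is the follow-up for a system that did not show equivalence and would probably enrol late, so the shortfall could fall mainly there.

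The evaluable/enrolled conflict is a separate labelling error. It does not lower power by itself, but it leaves the reader unsure which number the statistician calculated.

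**Working it through.** **Inputs.** All are from Sample Size Considerations except the last two: COV 12%; equivalence limit 10%; TOST in a two-period cross-over; alpha 0.025; power 80%; 33 evaluable; drop-out 10% (4 subjects); 37 enrolled; total 204. From Research Design: six sub-studies, with F conditional. Assumed here because the protocol does not state it: a true difference of 0.

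**Step 1: reproduce 33 and 37.** I read the 12% as the within-subject COV. With n subjects split over two sequences of n1 and n2, SE = 0.12 × √[½(1/n1 + 1/n2)] on n − 2 degrees of freedom. Power is the probability that the estimated difference lies between −0.10 + t·s and 0.10 − t·s, where s is the estimated SE and t is the 97.5th percentile of the t distribution, averaged over the distribution of s.

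- n = 32: power 0.794
- n = 33: SE = 0.12 × √[½(1/16 + 1/17)] = 0.0296, power 0.812

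So 33 is the first n to reach 80%, as the protocol says. Drop-out: 33/0.9 = 36.7, rounded up to 37, which is also 33 + 4. Both per-sub-study figures reproduce.

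**Step 2: try to reproduce 204.**

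| Sub-studies counted | × 37 enrolled | × 33 evaluable |
|---|---|---|
| 4 (A-D) | 148 | 132 |
| 5 (A-E) | 185 | 165 |
| 6 (A-F) | 222 | 198 |

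None is 204. Mixing 33s and 37s does not help: the nearest sums are 5×33 + 1×37 = 202 and 4×33 + 2×37 = 206. If 37 were the evaluable number, enrolment would be 37/0.9 = 41.1, rounded up to 42, giving 5 × 42 = 210 or 6 × 42 = 252.

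An even split of 204 over six gives 204/6 = 34, a number that appears nowhere in the protocol. Dividing by the stated enrolment gives 204/37 = 5.51, which is not a whole number of sub-studies.

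Differences: 222 − 204 = 18 short for A-F; 204 − 185 = 19 over for A-E.

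**Step 3: what 204 would mean for power.** These are illustrations, because the protocol does not say how 204 would be divided.

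| Case | Enrolled | Evaluable after 10% drop-out | Power |
|---|---|---|---|
| F not run, A-E at 37 | 185 in total | 33 each | at least 80% |
| All six, even split | 34 each | 34 × 0.9 = 30.6 | 0.752 (n = 30) to 0.773 (n = 31) |
| All six, even split, no drop-out | 34 each | 34 | 0.830 |
| A-E filled to 37, F gets the rest | 19 in F | 19 × 0.9 = 17.1 | 0.277 in F (n = 17) |

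The log scale with limits 0.9 to 1.1 gives nearly the same values: 0.814 at n = 33, 0.755 at n = 30, 0.776 at n = 31 and 0.285 at n = 17.

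**The case against.** The protocol calls 204 an estimate, and two of the six sub-studies are provisional. F depends on a failure elsewhere, and the doses compared in E are to be settled after Sub-Study D. One could read 204 as five full sub-studies plus a half allowance for F: 5.5 × 37 = 203.5, rounded up. The working target is also 37 per sub-study. No analysis uses 204, and nothing in the text calls it a cap, so a team that follows the 37 loses no power. The power figure for F is weaker still, since it assumes a two-period design that F may not have. Finally, if 204 is the enrolment actually intended, going to 222 is more than a wording change: it means up to 18 more people, each with an extra FDG scan.

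Much of this limits the consequence rather than the error. The half-allowance route appears nowhere in the protocol, and the sentence derives the total from six sub-studies at a fixed target, which leaves nothing to estimate. It does stand that the origin of 204 cannot be established, that the loss of power is conditional, that 222 is provisional until F is designed, and that a larger enrolment has a real cost if 204 was meant as a limit.

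**Conclusion.** The point holds. As written, 204 is inconsistent with 37 enrolled per sub-study: it is 18 below the 222 needed for A-F and 19 above the 185 needed for A-E. The per-sub-study figures of 33 and 37 are sound on the protocol's own assumptions, so the fault lies in the total.

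If F is not run, no power is lost. If all six run, 204 is the final enrolment and 10% drop out, 80% power is not expected in every sub-study. It would be about 75-77% in each under an even split, or about 28% in F if A-E are filled first. These powers rest on a true difference of 0, a within-subject COV of 12% and a two-period cross-over, and F may not fit the last of these.

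The 37 described as evaluable under Measurement / Instrumentation contradicts the 33 evaluable and 37 enrolled under Sample Size Considerations. Both places should be corrected, but neither error affects the validity of the planned analysis.

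**What to change.** 1. **Sample Size Considerations.** Replace the single total with two: 185 enrolled for Sub-Studies A to E, and 222 if Sub-Study F is run with 37. Add that F's number will be confirmed once its design is fixed, because Research Design describes comparison with both a lower and a higher dose whereas 37 was calculated for a two-period cross-over.
2. **If 204 is an intended ceiling,** keep it, show how it was obtained, say whether F is counted, and state that six sub-studies with 34 enrolled each would have about 75-77% power after 10% drop-out.
3. **Measurement / Instrumentation.** Change the 37 evaluable to 33 evaluable (37 enrolled).

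This costs edits to two paragraphs. The endpoint, margin, alpha and analysis do not change. If 204 was the enrolment actually planned and all six sub-studies run, the first option adds up to 18 participants, and the second accepts and declares a somewhat lower power.

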Participants in the research imaging will be predominately recruited from patients seen at the OSU Wexner Medical Center, including its outpatient facilities. Flyers will be available to patients that are seen in clinic offices typically referring patients for PET/CT examinations. This study will be published at clinicaltrials.gov. Potential participants will be identified by study team members at the time of the patient's standard of care imaging procedure. The patient population will include a variety of disease entities; therefore, enrollment will be monitored for relative distribution across disease categories, and the Principal Investigator's discretion will be utilized regarding the number of patients enrolled and their disease types in order to ensure a representative sample.

Randomization: Patients will be randomized in a 1:1 ratio to receive either standard of care FDG PET/CT dosing (481 MBq [13 mCi]) followed by the low dose FDG PET/CT (185 MBq [5 mCi]), or the low dose FDG PET/CT followed by the standard of care dosing using a randomized permuted block scheme in a blinded fashion. The block sizes will not be known to the investigator. No stratification factor will be included. We will, however, have the option of a randomization waiver if there are reasons that would otherwise delay patient care or prevent the patient from participating in the study.

Inclusion Criteria:

- Male and female patients greater than or equal to 18 years of age.
- Patients scheduled for a standard of care PET/CT scan.
- For female patients of child-bearing potential, the OSUWMC requirements for receiving the standard of care PET imaging agent and CT examination need to be met.

Since the patient will receive a standard of care scan as part of the protocol, we will follow the OSUWMC Imaging Services Departmental Policy and Procedure, which states that all females of child-bearing age (12-55 years old), will receive urine HCG pregnancy testing within seven days prior to imaging. While the policy also states that patients may refuse the testing by completing the pregnancy testing refusal form, we will not accept the form for this trial. All female patients of child-bearing age will be required to have the urine HCG test on the day of imaging or no more than 7 days prior to the imaging.

Exclusion Criteria:

- Participants who are pregnant or lactating.
- Prisoners.
- Participants incapable of giving informed consent.

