All paper and electronic data/information will be coded prior to any review or analysis. All paper documents will be stored in a locked file cabinet with limited access in the Department of Radiology at The Ohio State University. All electronic data obtained through PACS or IHIS will be stored in a coded manner on password protected servers with limited access in the Department of Radiology at The Ohio State University. No individual identities will be used in any publications resulting from this study. Officials from examining bodies such as the U.S. Food and Drug Administration or NIH may inspect records pertaining to this study.

Internal Validity

This crossover design is necessary to blind the patient and the technologist to be unbiased during the performance of the imaging, as motion artifacts, positioning, and other aspects can influence image quality to some extent.

Data Analysis

Our primary hypothesis is that the SUVmax will be equivalent between standard of care dosing (13 mCi) and the low dose (5 mCi) in each PET/CT system. The two one-sided tests procedure (TOST) will be used to test the equivalence of SUVmax at 75 min post injection between the standard care of dosing and the low dose. As SUVmax is known to have lognormal distribution, the data will be log-transformed before all analysis. Holm-Bonferroni method will be used to adjust for multiple ROIs. The McNemar-Bowker's test will be used to evaluate the inter-reader reliability in image quality measured from 1-10 scale between every two readers. The average scores will be calculated among those 3 readers. The TOST test will be used to

test the equivalence in the average score of image quality between the standard care of dosing and the low dose.

The percentage of change in SUVmax measured from 60 min to 75 min will be tested first for equivalence between the standard of care dosing and the low dose target ROI in each PET/CT system. Then the SUVmax measured at 60 min will be compared to SUVmax measured at 75 min within standard care of dosing and the low dosing groups, respectively.

V. Bibliography

- 3. Miletich, RS. Positron emission tomography for neurologists. *Neurol Clin.* Feb 2009;27(1):61-88.

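### Scan order is randomised with no stratification factor although each PET/CT system is its own crossover; the protocol should provide a permuted-block list per sub-study (minor)

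*Protocol*

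**What the plan says.** All references are to section IV (Procedures) of the protocol.

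- **Randomization.** "Patients will be randomized in a 1:1 ratio to receive either standard of care FDG PET/CT dosing" first or second, "using a randomized permuted block scheme in a blinded fashion". No block size is given. Then: "The block sizes will not be known to the investigator. No stratification factor will be included". The next sentence adds: "We will, however, have the option of a randomization waiver".
- **Sample Size Considerations.** "The subjects imaged at each of the four PET/CT systems will treated as its own sub-study". Each sub-study has 33 evaluable and 37 enrolled patients, for a TOST on a two-period crossover with 80% power, alpha 0.025, a coefficient of variation of 12% and an equivalence limit of 10%.
- **Measurement / Instrumentation.** The sub-studies are described as independent by device, and the aim is "to prove equivalency using four distinct platforms in parallel".
- **Data Analysis.** The primary hypothesis is equivalence of SUVmax between "standard of care dosing (13 mCi) and the low dose (5 mCi) in each PET/CT system".

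The protocol does not say whether the systems share one randomisation list, and it gives no enrolment schedule by system.

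**The concern.** Permuted blocks balance allocation only along the list from which they are drawn. The unit of inference here is the single PET/CT system, but the one factor that would align the blocks with that unit is ruled out by an explicit sentence. If consecutive entries of a shared list go to patients on different scanners, order within a scanner is left largely to chance.

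Two things are at stake, depending on the analysis. If period is fitted, unequal order groups cost precision, and the plan has only about one point of power to spare. If period is not fitted, part of any difference between first and second visit enters the comparison of low with standard dose. Because a difference between systems could lead to different dose-reduction schemes (Measurement / Instrumentation), each system's result matters by itself. An analysis plan written later can adjust for period, but it cannot restore balance in an allocation already made.

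**Working it through.** **Inputs from the protocol.** 33 evaluable per system; CV 12%, taken as within-patient SD s = 0.12; limit ±0.10; alpha 0.025, used for each one-sided test; 1:1 order. **Assumed.** True difference 0; one list shared by four systems of 33 patients; random intermixing of arrivals; block size 2, 4, 6 or 8.

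**1. Reproducing the planned sample size.** For a two-period crossover with order groups n1 and n2:

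SE = s × √[½(1/n1 + 1/n2)], with n1 + n2 − 2 degrees of freedom.

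At 17:16, SE = 0.12 × √[½(1/17 + 1/16)] = 0.0296. TOST power, integrated over the distribution of the estimated SD, is 81.2%. The smallest N reaching 80% is 33, as stated. Dropout: 33/0.90 = 36.7, rounded up to 37, also as stated.

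**2. How unequal the order groups could become.** Simulating one unstratified list under these assumptions:

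| Split among 33 | A given system | At least one of four |
|---|---|---|
| 20:13 or worse | about 22–23% | about 57% |
| 22:11 or worse | about 4–5% | about 15% |

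Block size from 2 to 8 makes almost no difference.

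**3. Cost if period is fitted.** The effective sample size is 4·n1·n2/N.

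| Split | SE | Effective N | Power |
|---|---|---|---|
| 17:16 | 0.0296 | 33.0 | 81.2% |
| 20:13 | 0.0302 | 31.5 | 78.6% |
| 22:11 | 0.0313 | 29.3 | 74.2% |

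Averaged over the simulated splits, power is about 79.9%, a loss of 81.2 − 79.9 = 1.3 points.

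**4. Cost if period is not fitted.** A period effect π shifts the dose contrast by π(n1 − n2)/N. The protocol gives no period effect, so 2% and 5% are assumed.

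| Split | Share of π | Shift, π = 2% | Shift, π = 5% |
|---|---|---|---|
| 20:13 | 7/33 = 0.21 | 0.4 points | 1.1 points |
| 22:11 | 11/33 = 0.33 | 0.7 points | 1.7 points |

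At the affected limit, the simulated one-sided type I error rises from a nominal 2.5% to about 3.2% (π = 2%) or 4.6% (π = 5%) at 20:13, and to about 4.0% or 6.8% at 22:11.

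**5. With one list per system.** With blocks of 4, the two order groups of a system can never differ by more than 2 at randomisation.

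**The case against.** The strongest reply is that the Randomization paragraph does not say that one list spans the scanners. Measurement / Instrumentation calls the sub-studies independent by device, so the exclusion of stratification may mean none within a sub-study. The planned Sub-Studies E and F support this: their dose comparisons differ from the 481 versus 185 MBq scheme, so they need some scheme of their own. If lists are already kept per sub-study, the blocks do their work and only the wording is at fault. Intermixed accrual is also an inference, since the words about platforms in parallel describe evaluation rather than an enrolment calendar. If one list with blocks of 4 filled the systems one after another, a system of 37 could be no worse than 20:17. These points stand, so the splits above are conditional.

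A reader might go further and infer that the dose comparison is biased. The protocol does not support that. Every patient is their own control, so bias needs both a real period effect and an analysis that ignores period. Data Analysis names no period term, but that detail commonly belongs in the SAP, which is not at hand, and its absence is not counted here. Research Design also aims for a second scan one to four days after the first, with two weeks only as the outer limit, which restricts the scope for change between visits. Nor does the point show that 33 patients are too few: that figure reproduces.

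What remains is that the protocol does not merely leave the matter open. It rejects any stratification factor, and nowhere states that lists are separate.

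**Conclusion.** The point holds in a limited form and is minor. As written, the randomisation rule does not secure 1:1 order balance within the unit in which equivalence is tested. Given one shared list and intermixed enrolment, a noticeable imbalance (20:13 or worse) in at least one of the four systems is more likely than not, at about 57%. Its cost is small: about 1 point of power on average and 2.6 points at 20:13 (81.2 − 78.6) if period is fitted, or a shift of about 0.4 to 1.1 points at 20:13 for an assumed 2 to 5% period effect if it is not. The 22:11 case, with 74.2% power, occurs in only about 4 to 5% of systems. If separate lists are in use, none of this arises and the sentence is simply misleading.

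**What to change.** In the Randomization paragraph, replace the sentence that excludes any stratification factor with a statement that a separate permuted-block list is generated for each sub-study (stratified by PET/CT system), with block sizes still concealed and no further stratification factor. If this is already the practice, correct the sentence to say so.

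The cost is one list per sub-study instead of one overall. No extra patients or visits are needed and the sample size does not change. The system must be assigned before the order is drawn; the protocol does not state when that happens, so the same sentence should make it explicit.

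The change secures balance at randomisation only. The randomisation waiver and the four expected dropouts per sub-study can still unbalance the analysed set, so achieved order should be reported by sub-study, with waived patients identified.

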Protocol Title: Validating Low FDG Dose PET/CT compared to current Standard of

Care Dose PET/CT

Protocol Project Number: RP0308

Protocol Date: May 22, 2017

Principal Investigators:

[name], PhD

Vice Chairman and Professor, Department of Radiology

Novartis Chair of Imaging Research

The Ohio State University

[name]

[name]

[contact]

[contact]

E-Mail: [contact]

[name], DABR

Assistant Professor of Radiology

Diagnostic Medical Physicist

[name]

[name]

[contact]

[contact]

E-Mail: [contact]

I. Overview

Positron Emission Tomography/Computed Tomography (PET/CT) imaging using ¹⁸F-FDG is an important, commonly used cancer, neuroscience and cardio-vascular imaging methodology to detect disease and to monitor therapeutic interventions. While considerable technological progress of PET/CT systems has occurred over the last decade, we have not re-evaluated the ability to potentially reduce the radiation burden of the used PET imaging pharmaceutical (FDG).

This early phase trial intends to accomplish the following:

- to validate that the radiation dose burden from the PET imaging pharmaceutical (FDG) can be reduced by more than 50% from the current standard of clinical care (SOC) level without affecting the diagnostic ability;
- to confirm that a low dose approach will be feasible for response assessment;
- to validate that the difference in FDG uptake between imaging 60 min +/- 10 min post injection and 75 min +/- 10 min post injection is independent/equivalent of the injected FDG dose
- to validate a simulation methodology to streamline future dose finding studies for PET imaging pharmaceuticals.

II. Objectives

Aim 1: To validate equivalency of low dose FDG PET/CT (185 MBq [5 mCi]) compared to current standard of care FDG PET/CT dosing (481 MBq [13 mCi]).

Aim 2: To validate that the difference in FDG uptake between imaging 60 min post injection and 75 min post injection is independent/equivalent of the injected FDG dose

Aim 3: To validate equivalency of simulated FDG dose PET/CT images to effective dose reduced FDG PET/CT images

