For secondary assessments, we will determine by three independent, blinded readers the image quality for a diagnostic interpretation with a linear 10 cm scale from exceptional to unacceptable. We will use the same approach to assess the diagnostic confidence and occurrence of image artifacts and to allow for any additional comments desired. For the read assessment, each PET/CT exam will be individually assessed in a randomized order. Upon completion of this assessment and after a duration of several weeks, a matched pair assessment will be performed to assess equivalency during a side-by-side comparison using the same assessment scales. If those assessments confirm equivalency, we plan to add a full diagnostic read of each exam separately with blinded dosing information.

For this Phase I study, we believe that performing intra-individual comparisons on the same PET/CT system is the only way to get unconfounded, objective assessment of the equivalency of dose reduction. In case we would find difference between the four different PET/CT systems, different dose reduction schemes might be necessary.

While we cannot evaluate in this trial the equivalency for response assessment of therapy between the low dose and current standard of care dose, we do have at least the ability to evaluate that the difference in FDG uptake between the whole body sweep at 60 min +/- 10 min and 75 min +/- 10 min for the target regions is not impacted by dose. While this is our hypothesis we want to evaluate, we will at the same time gain insight into the intra-individual variability in FDG uptake within such a 15 min +/- 10 min window. The current guidelines recommend that the PET/CT whole body sweep be performed 60 min +/- 10 min post injection, giving a 20 min window to start the whole body sweep [Shankar]. Current clinical practice however is favoring imaging around 75 min p.i. which leads to a considerable number of protocol deviations in clinical trials.

As Imaging Core Laboratory for a large number of trials which include PET imaging, we see that the protocol deviation rate in time post injection is consistently the highest with rates of 15% to 40% depending on protocol, most frequently however in the time frame of 70 to 80 min post injection. By adding this aim to the protocol, we can answer another burning clinical/scientific question without adding any additional radiation exposure to the patient.

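### Does wording the primary endpoint as SUVmax variation under 10% promise per-patient agreement that the planned test of means cannot show?

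*Protocol*

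**What the plan says.** All references are to the protocol; no SAP is at hand.

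- **Endpoint (IV. Procedures, Measurement / Instrumentation).** The primary endpoint is a confirmation, by statistical means, that "the SUV max measured in the regions of interest (ROI) in the target region will reveal a variation of less than 10"%. The sentence names no mean, ratio or confidence interval. The sentence after it gives a sample size and sends the reader to the statistical section.
- **Design (Sample Size Considerations).** "we assume that the coefficient of variation (COV) is 12% and the equivalence limit is 10"%. The stated 33 evaluable patients are to give "80% power in an equivalence test of means using two one-sided tests (TOST) on data from a two-period cross-over design", at an alpha of 0.025.
- **Analysis (Data Analysis).** The primary hypothesis is equivalence of SUVmax between the two doses on each system. "The two one-sided tests procedure (TOST) will be used to test the equivalence of SUVmax at 75 min post injection". "As SUVmax is known to have lognormal distribution, the data will be log-transformed before all analysis". For several regions, "Holm-Bonferroni method will be used to adjust for multiple ROIs".
- **Response assessment.** The Overview lists among the trial's intentions "to confirm that a low dose approach will be feasible for response assessment". Measurement / Instrumentation later says: "While we cannot evaluate in this trial the equivalency for response assessment of therapy between the low dose and current standard of care dose". It goes on to offer only a check that the 60-to-75 min uptake change does not depend on dose.

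**The concern.** Sample Size Considerations uses the word variation for scatter (a CV of 12%) and a separate term for the 10% margin. The endpoint sentence attaches variation to the 10%. Taken literally, it asks for scatter below 10% in a design that assumes 12%, or for each patient's two scans to agree within 10%. A TOST of means answers neither question, because it can pass while many individual pairs differ widely.

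Under Benefits, the site says it will change its standard of care if the low-dose examination is found equivalent. A reader could therefore worry that a passed test would be reported as per-patient agreement. The Overview bullet raises a similar worry, since it announces a result on response assessment that the protocol later says it cannot deliver.

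**Working it through.** **Inputs.** From Sample Size Considerations: CV 12%, limit 10%, alpha 0.025 (taken as the level of each one-sided test), 80% power, N = 33, two-period crossover. From Data Analysis: log scale. Assumptions: 12% is the within-subject CV (the protocol does not say which CV it is), and the true dose effect is zero.

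**1. Reproduce N.**
- Within-subject log SD = √ln(1 + 0.12²) = 0.1196.
- SD of the paired log difference = √2 × 0.1196 = 0.1691.
- Exact crossover TOST power (df = N − 2):

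| Meaning of 10% on the ratio scale | Power at N = 33 | Smallest N for 80% |
|---|---|---|
| 0.90 to 1.111 | 86.8% | 30 |
| 0.90 to 1.10 | 81.4% | 33 |
| 1/1.1 to 1.1 | 76.0% | 36 |

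An untransformed margin of ±0.10 with SD 0.12 also gives 33 (81.3%). If 12% were the SD of the paired difference, 18 patients would be enough. The stated 33 therefore fits a within-subject CV with limits of 0.90 to 1.10, or ±0.10 untransformed.

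**2. What the test shows.** With an observed ratio of 1.00:
- Standard error = 0.1691/√33 = 0.0294.
- Half-width = 2.04 × 0.0294 = 0.060.
- 95% confidence interval = exp(±0.060) = 0.94 to 1.06, so the TOST passes.

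**3. What a per-patient reading would need.**
- 95% limits of agreement = exp(±1.96 × 0.1691) = 0.72 to 1.39.
- Share of patients outside 10%: 53% (0.90 to 1.111), 55% (0.90 to 1.10) or 57% (1/1.1 to 1.1).
- For 95% of patients to lie within 10%, the CV would have to be ln(1.1)/(1.96√2) = 3.4%, or −ln(0.9)/(1.96√2) = 3.8%.
- With an observed mean difference of zero, the TOST still passes at a paired SD up to 0.10 × √33/2.04 = 0.28 (within-subject about 20%). About 28% of patients would then lie within 10%.

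The individual and average readings are thus clearly different quantities.

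**4. Which reading the protocol plans.** The 10% appears once more, in Sample Size Considerations, as the limit of an equivalence test of means. Data Analysis then names the TOST for the primary hypothesis. No section sets a share of patients within 10%, limits of agreement or any other individual criterion. Only the average reading has a test, a margin and a sample size, and these agree with one another.

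**5. Response assessment.** Three of the four Overview bullets correspond to Aims 1 to 3 in II. Objectives: dose equivalence, uptake change by dose, and simulated images. The response-assessment bullet corresponds to none. Data Analysis has no comparison on therapy response, only the 60-to-75 min change.

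**The case for a change.** The strongest case for a change has three parts.

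First, the endpoint sentence is the only one labelled as the primary endpoint, so it is the one most likely to be quoted. Its wording is looser than the test behind it, and that stands as an editorial remark. It does not create a second analysis: the sentence itself speaks of statistical confirmation and points to the statistical section, which settles the meaning. The figures in step 3 describe ordinary scan-to-scan repeatability at the assumed CV. They show no low-dose fault and no error in the test or in N.

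Second, 10% on a log scale has three possible meanings, with power from 76% to 87%. This is true, but exact ratio limits and the interval level after Holm adjustment are commonly fixed in a SAP. The protocol's own N points to 0.90 to 1.10.

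Third, a change in care hangs on the word equivalent. The Benefits statement speaks of the examination, however, and names neither SUVmax nor the 10% sentence. Measurement / Instrumentation adds three blinded readers, image quality, diagnostic confidence, artifacts and a side-by-side comparison. If those assessments confirm equivalence, it also plans a full diagnostic read.

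The conflict over response assessment is real, although feasibility is a weaker claim than equivalence. The later passage already withdraws the stronger claim openly.

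Limits of agreement would be a harmless descriptive extra. They mix any dose effect with repeatability, so they would not settle per-patient equivalence.

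**Conclusion.** The concern is right that a passed TOST would not show per-patient agreement within 10%. At a within-subject CV of 12%, more than half of patients would fall outside that range with no dose effect at all. It does not follow that the plan is wrong. Read together, the protocol's sections define average equivalence of log SUVmax within a 10% limit, and 33 patients give about 81% power for it with limits of 0.90 to 1.10. An analyst following the plan would report a geometric mean ratio with its confidence interval and claim no more.

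The endpoint sentence is a slip of wording, and the Overview bullet is a stray statement disclaimed elsewhere. Correcting either would change no test, sample size, data collection or supportable conclusion.

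This rests on reading 12% as the within-subject CV, which the protocol does not state but which reproduces 33, and on the usual practice of fixing exact ratio limits in the SAP.
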